2. PROTOCOL SUMMARY

2.1 Study design and conduct

This is a local, prospective, multicentre, non-interventional, observational study in adult patients with T2DM diagnosis.

Due to the observational design, patient visits to the referring physician are not pre-specified by the study protocol, but will follow usual clinical practice. All patient-care decisions, including diagnostic and therapeutic interventions, will be made by and conducted at the discretion of the participating study physicians according to their clinical judgment and the local standard of medical care.

[figure not shown]
Start of the study is defined as the date of the start of data collection (first patient signed ICF for data collection).

End of the enrolment (Last Patient First Visit) is defined as the date when the last patient signs ICF and enrolled in the study.

End of the patient observation (Last Patient Last Visit) is defined as the last date when the patients are observed in the scope of the study.

End of study (end of data collection) is defined as the date when the last data point is collected. Up to this date all the CRFs should be completed and all the data clarifications (queries) should be done.

The study is considered to be completed after the database is closed, the final statistical analysis is performed and the study report is written. The study report must be signed within 12 months after the collection of the last data point.

It's planned that interim statistical analysis of study data will be performed as soon as 350 first study patients have completed the study by achieving final study visit or discontinuing their participation.

Term	Baseline visit (V1)	Observational visit (V2)	Final visit (V3)
Inclusion/exclusion criteria	X		
Signed Informed consent form	X		
Date of visit	X	X	X
Demographic information	X		
Medical history including history of DM2T	X		
Concurrent medical conditions	X		
Physical examination and vital signs*	X	X	X
Study medication	X	X	X
Laboratory tests and instrumental exams*	X	X	X
Concomitant treatment (including DM2T treatment)	X	X	X
Healthcare resources utilization		X	X
Adverse events		X	X

For study details and study assessment's schedule see the Protocol of the Study.

2.2 Study objectives

2.2.1 Primary objective

1. The primary objective is to evaluate the effect of Vipidia® on glycosylated hemoglobin (HbA1c) level dynamics in patients with diabetes mellitus type 2 (V3).

2.2.2 Secondary objectives

The secondary objectives for this study are as follows:

1. To evaluate the effect of Vipidia® on glycosylated hemoglobin (HbA1c) level dynamics in patients with diabetes mellitus type 2 (V3) in dependence on clinical characteristics
2. To describe the real-world clinical response to treatment with Vipidia® as assessed by glycosylated hemoglobin (HbA1c) level reduction to the goal <7.0%;
3. To evaluate the effect of Vipidia® on glycosylated hemoglobin (HbA1c) level dynamics in patients with diabetes mellitus type 2 over time (V1-V2-V3);
4. To evaluate the proportion of patients with diabetes mellitus type 2 and marked hyperglycemia (V2);
5. To evaluate the effect of Vipidia® on fasting plasma glucose dynamics in patients with diabetes mellitus type 2 over time (V1-V2-V3);
6. To evaluate changes in weight during Vipidia® treatment period (V1-V2-V3);
7. To evaluate changes in metabolic parameters (pre- and postprandial glycemia, total cholesterol triglycerides, low density lipoproteins, high density lipoproteins) during Vipidia® treatment period (V1-V2-V3);
8. To estimate proportion of patients with diabetes mellitus type 2 who decrease in HbA1c $\geq 0.3\%$

over time (V1-V2-V3);

9. To estimate proportion of patients who used healthcare resources (rate of hospitalization, reason, emergency, emergency room visits, and physician office visits; in case of hospitalization, length of stay, reason, and urgency [urgent/not urgent]).

2.2.3 Safety objectives

The safety objectives for this study are as follows:

1. To describe patient incidence and type of adverse events as assessed by adverse drug reactions (ADRs), serious AEs (SAEs), and AEs of special interest (AESIs) to treatment with Vipidia®;
2. To describe incidence of newly diagnosed co-morbidities and complications.

2.2.4 Exploratory objectives

The exploratory objectives for this study are as follows:

Company Confidential Information

2.3 Study variables

2.3.1 Efficacy variables

The study has primary endpoint: Change from baseline in glycosylated hemoglobin (HbA1c) level on Vipidia® therapy (V3).

Secondary endpoints of this study will be:

1. Change from baseline in glycosylated hemoglobin (HbA1c) level on Vipidia® therapy (V3) in subgroups with different clinical characteristics.
2. Proportion (%) of patients with diabetes mellitus type 2 who assessed by glycosylated hemoglobin (HbA1c) level reduction to the goal <7.0% by V3;
3. Change from baseline in glycosylated hemoglobin (HbA1c) level on Vipidia® therapy over time (V1-V2-V3);
4. Proportion (%) of patients with marked hyperglycemia (V2) (Marked Hyperglycemia is defined as fasting plasma glucose higher than or equal to 11 mmol/L);
5. Change from baseline in fasting plasma glucose level on Vipidia® therapy over time (V1-V2-V3);
6. Change from baseline in weight during Vipidia® treatment period (V1-V2-V3);
7. Change from baseline in metabolic parameters (pre- and postprandial glycemia, total cholesterol triglycerides, low density lipoproteins, high density lipoproteins) during Vipidia® treatment period (V1-V2-V3);
8. Proportion (%) of patients with diabetes mellitus type 2 who decrease in HbA1c $\geq 0.3\%$ over time (V1-V2-V3);
9. Proportion (%) of patients who used healthcare resources - rate of hospitalization, reasons, emergency, emergency room visits, and physician office visits; in case of hospitalization, length of stay, reason, and urgency (urgent/not urgent).

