5. STATISTICAL / ANALYTICAL ISSUES

Visit windows

In accordance with the protocol, due to the non-interventional study design it's not possible to appoint exact times for the study visits, although it is expected that the period of observation will be approximately 6 months. The frequency of the visits will be assigned by each physician according to their routine practice. It is anticipated that the patients will visit their physician every 3 months and more often at the beginning.

So, for the analysis and summary of clinical laboratory, efficacy, and safety data in case of this analysis/summary performed on "by visit" base. In the event of multiple values for an assessment within an analysis window, the value closest to the scheduled visit date will be used for analyses. If two values tie as closest to the time point (for example, one value is before and the other value is after the time point), then the later value will be selected as the analysis value.

Analysis Window	Start	End	Target	Assessment to be used if duplicates
Baseline visit	<1			NA
Month 3 (Visit 2)	0	135	90	Closest to target day, if equidistant use later result.
Month 6 (Visit 3)	136	NA	180	

The definition for the study days included in each study window is defined as below:

Treatment Day prior to first dose = Visit Date – Date of First Dose

Treatment Day on or after first dose = Visit Date – Date of First Dose + 1

Adjustments for Covariates

No specific adjustments for covariates will be made in all statistical analyses, unless specified otherwise per-analysis level.

Handling of Dropouts or Missing Data

Missing efficacy outcomes will be assumed to be missing at random (MAR) and thus will not be imputed in the primary analysis. However if greater than 1% of all primary/secondary outcomes that should be available for analysis are missing, a sensitivity analysis will be undertaken in addition to the primary MAR analysis.

This sensitivity analysis will include an evaluation of the results of models developed under the assumptions of:

- 1) last observation carried forward;
- 2) worst extreme case imputation and;
- 3) regression model imputation using all available information.

Outlier identification

During data Quality Control outlier identification will be performed using adjusted Z-score method (Iglewicz and Hoaglin, 1993).

$$M_i = \frac{0.6745(x_i - \bar{x})}{MAD}$$

where MAD - Median absolute deviation, \bar{x} - median.

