9.2. Statistical Analysis of the Secondary Efficacy Variables

Secondary and exploratory outcomes will be analysed using descriptive statistics and frequencies and percentages as follows:

9.2.1. Change from baseline in glycosylated hemoglobin (HbA1c) level on Vipidia® therapy over time (V1-V2-V3) will be summarized using relevant descriptive statistics and analyzed with mixed model with repeated measures using clinical characteristics as independent factors; 9.2.2. Proportion (%) of patients with marked hyperglycemia (V2) (Marked Hyperglycemia is defined as fasting plasma glucose higher than or equal to 11 mmol/L) will be described and presented in summary tables using absolute frequencies and percentages as well as 95% confidence intervals; 9.2.3. Change from baseline in fasting plasma glucose level on Vipidia® therapy over time (V1-V2-V3) will be summarized using relevant descriptive statistics and analyzed with mixed model with repeated measures using clinical characteristics as independent factors; 9.2.4. Change from baseline in weight during Vipidia® treatment period (V1-V2-V3) will be calculated and presented in summary tables using descriptive statistics for continuous variables;

9.2.5. Change from baseline in metabolic parameters (pre- and postprandial glycemia, total cholesterol triglycerides, low density lipoproteins, high density lipoproteins) during Vipidia® treatment period (V1-V2-V3) will be summarized using relevant descriptive statistics and analyzed with mixed model with repeated measures using clinical characteristics as independent factors; 9.2.6. Proportion (%) of patients with diabetes mellitus type 2 who decrease in HbA1c $\geq 0.3\%$ over time (V1-V2-V3) will be

described and presented in summary tables using absolute frequencies and percentages as well as 95% confidence intervals;9.2.7. Healthcare resources utilization: rate of hospitalization, reasons, emergency, emergency room visits, and physician office visits; in case of hospitalization, length of stay, reason, and urgency (urgent/not urgent) will be described and presented in summary tables using absolute frequencies and percentages as well as 95% confidence intervals:9.2.8

Company Confidential Information

Company Confidential Information

Company Confidential Information

Company Confidential Information

Company Confidential Information

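### Healthcare use is reported only as counts and percentages of patients over unequal follow-up, with no time base for the hospitalisation rate, no rule on which office visits count, and length of stay worded as a percentage

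*SAP*

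**What the plan says.** Section 2.3.1, item 9, defines the endpoint as "Proportion (%) of patients who used healthcare resources - rate of hospitalization, reasons, emergency, emergency room visits, and physician office visits", followed by length of stay, reason and urgency for hospitalisations. Objective 9 in section 2.2.2 likewise asks for a proportion of patients.

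Section 9.2.7 gives one method for the whole list. Its closing words are "length of stay, reason, and urgency (urgent/not urgent) will be described and presented in summary tables using absolute frequencies and percentages", with 95% confidence intervals. It gives no person-time, no fixed time horizon and no number of contacts per patient.

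The schedule in section 2.1 marks the row "Healthcare resources utilization" at V2 and V3 only. On timing, the same section says that "patient visits to the referring physician are not pre-specified by the study protocol, but will follow usual clinical practice". Section 5 (Visit windows) adds that "The frequency of the visits will be assigned by each physician according to their routine practice" and that "it is expected that the period of observation will be approximately 6 months". Its window table assigns day 136 onward to Visit 3, with a target of day 180 and no upper limit. Section 2.4 allows for a 25% dropout.

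Section 3 (Summary of study data) gives every continuous variable n, mean, SD, median, quartiles and range. It bases percentages on patients with non-missing data.

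**The concern.** There are three separate problems.

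1. **No time base.** The chance that a patient has at least one hospitalisation or emergency visit rises with the time observed. When that time varies, a crude percentage mixes use with length of observation. The endpoint also promises a hospitalisation rate, and section 9.2.7 supplies no denominator for one.
2. **Office visits.** Healthcare use is recorded at V2 and V3, which are themselves visits to the physician. The SAP does not say whether they count as office visits. If they do, everyone in the denominator has at least one.
3. **Length of stay.** This is a continuous quantity, but section 9.2.7 puts it under counts and percentages, which conflicts with section 3.

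What is at stake is the reading of a descriptive secondary endpoint. Sections 9.3.9 and 9.3.10 also analyse secondary outcomes by diabetes duration and in patients without therapy in the last 12 weeks. If follow-up differs between such groups, their percentages will differ even where use is the same.

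**Working it through.** **The plan's own figure.** The SAP gives no figure for this endpoint. The dropout allowance in section 2.4 reproduces: 1052 / (1 − 0.25) = 1402.7, rounded up to 1403, as stated.

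**Inputs.** From the SAP: 25% dropout, target follow-up of about 6 months, Visit 3 window from day 136, target day 180. Assumed, because the SAP gives none: constant event rates of 0.1, 0.2 and 0.5 per patient-year, all leavers going at 3 months with their use recorded up to then, and day 270 as an illustration of a late V3.

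**Formula.** Proportion with at least one event by time t (in years) = 1 − exp(−rate × t).

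**Effect of dropout.** Mixed proportion = 0.75 × (6-month value) + 0.25 × (3-month value).

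| Rate per year | 3 months | 6 months | Mixed |
|---|---|---|---|
| 0.1 | 2.47% | 4.88% | 4.28% |
| 0.2 | 4.88% | 9.52% | 8.36% |
| 0.5 | 11.75% | 22.12% | 19.53% |

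Example at 0.1: 0.75 × 4.88 + 0.25 × 2.47 = 4.28. The relative loss is about 12% at each rate (4.28/4.88 = 0.88; 19.53/22.12 = 0.88).

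**Effect of the open V3 window** (t = day / 365.25).

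| Rate per year | Day 136 | Day 180 | Day 270 | Day 270 / day 136 |
|---|---|---|---|---|
| 0.1 | 3.66% | 4.81% | 7.13% | 1.95 |
| 0.2 | 7.18% | 9.39% | 13.74% | 1.91 |
| 0.5 | 16.99% | 21.84% | 30.90% | 1.82 |

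**A person-time rate on the same data.** In the dropout example at 0.1 per year, mean follow-up is 0.75 × 0.5 + 0.25 × 0.25 = 0.4375 years. Expected events per patient are 0.1 × 0.4375 = 0.04375, and 0.04375 / 0.4375 = 0.1. The rate does not move with follow-up.

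**Office visits.** If V2 and V3 count, each patient with healthcare-use data has at least one. With 1052 such patients the result is 1052/1052, and the exact 95% lower limit is 0.025^(1/1052) = 99.65%, whatever the true use.

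**Length of stay.** Section 9 sends efficacy variables to the section 3 summaries unless stated otherwise. Section 9.2.7 does state otherwise, and names a format that does not suit a duration.

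**The case against.** The strongest reply is that the endpoint still works. The components are named one by one, and no section merges them into a composite. The percentages for hospitalisation and emergency visits are not saturated (2.5% to 22% over 3 to 6 months at the assumed rates) and remain informative. This stands. A reader might infer that the endpoint cannot describe healthcare use at all, or that objective 9 goes unanswered. The SAP does not support that.

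Second, the 100% figure is conditional. It needs V2 and V3 to count as office visits, and the SAP leaves this open; the rule may sit in the protocol or CRF. This also stands. The point is that the result cannot be read without the rule.

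Third, the size rests on assumed rates, and day 270 is not in the plan. Setting patients stopped at day 90 against patients seen to day 270 would give about a threefold spread, but that compares two hypothetical cohorts. With the plan's own 25% dropout the shift at 0.1 per year is 0.6 percentage points. Section 8 also summarises exposure, so readers will have a rough idea of time at risk.

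Fourth, there is no comparator, so no treatment contrast is biased. Subgroup distortion requires follow-up to differ between subgroups, which the SAP does not show. The interim has no subgroup analyses, and the final results prevail over it.

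These replies limit the harm. They do not supply a denominator for the rate or a proper summary for length of stay.

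**Conclusion.** The point holds in a limited form. Crude percentages over unequal follow-up mix use with observation time, the promised hospitalisation rate has no time base, the counting of office visits is undefined, and the wording on length of stay conflicts with section 3.

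The effect of dropout alone is modest: about 12% in relative terms if 25% of patients leave at 3 months. The open V3 window could matter more, since the proportion nearly doubles at the lower rates if some patients are seen at day 136 and others at day 270. How widely V3 dates will spread cannot be known from the SAP. All these sizes assume a constant event rate between 0.1 and 0.5 per patient-year. The absolute figures move with the rate, while the relative changes are similar across that range.

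The harm is to interpretation and to subgroup comparison within a descriptive secondary endpoint. Adding rates improves on the stated method at little cost.

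**What to change.** In section 2.3.1 item 9 and section 9.2.7:

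- Keep the proportion of patients, which objective 9 asks for, and report it for each component separately.
- Add events per patient-year with 95% confidence intervals for hospitalisations, emergency visits and office visits. Count person-time from first dose to the last visit at which healthcare use was recorded, and include early leavers up to that visit. A later contact should not extend it, because use was not recorded then.
- Report office visits as a number per patient-time. State whether V2 and V3 count, or show visits beyond V2 and V3 separately. In a non-interventional study V2 and V3 are real care, so they need not be discarded.
- Summarise length of stay with the continuous statistics of section 3. Keep counts and percentages for reason and urgency.

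**Cost.** SAP wording and slightly more programming. Visit dates and dosing information are already part of the plan. The rates also need the number of events per patient, and the SAP does not show whether the CRF records this for emergency and office visits, so it should be checked first. The rates assume a roughly constant event rate over follow-up, which should be stated beside them.

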2.3.2 Safety variables

The safety outcome measures for this study are as follows:

1. Patient incidence and type of adverse events as assessed by adverse drug reactions (ADRs), serious AEs (SAEs), and AEs of special interest (AESIs) to treatment with Vipidia®;
2. Incidence of newly diagnosed co-morbidities and complications.

2.3.3 Other variables of interest

Other variables of interest (exploratory endpoints) for this study are:

Company Confidential Information

[figure not shown]
2.4 Sample size and power

Sample size was calculated for the primary objective of the study: to evaluate the effect of Vipidia® on glycosylated hemoglobin (HbA1c) level dynamics in patients with diabetes mellitus type 2 (V3). Sample size was calculated using SAS 9.3 proc power procedure (power for Confidence Interval for Paired Mean Difference as for accuracy of parameter estimation) for following parameters (fixed scenario elements):

Fixed Scenario Elements	
Distribution	Normal
Method	Exact
Correlation	0.35
Nominal Prob(Width)	0.9
Number of Sides	2
Alpha	0.05
Prob Type	Conditio nal

Standard deviation was assessed based on S. Del Prato et. al study and was considered to be at most 0.70% (for glycosylated hemoglobin level dynamics). To determine required number of patients values from 0.60% to 0.70% were taken. Desired half-wide for parameter estimation was set as range between 0.05 – 0.1. Following required number of pairs were calculated:

Computed N Pairs				
Ind ex	Half-Width	Std Dev	Actual Prob(Width)	N Pairs
1	0.05	0.60	0.904	770
2	0.05	0.65	0.904	899
3	0.05	0.70	0.900	1037
4	0.06	0.60	0.904	542
5	0.06	0.65	0.903	632
6	0.06	0.70	0.903	729
7	0.07	0.60	0.906	404
8	0.07	0.65	0.902	470
9	0.07	0.70	0.904	542
10	0.08	0.60	0.902	313
11	0.08	0.65	0.907	365
12	0.08	0.70	0.905	420
13	0.09	0.60	0.905	251
14	0.09	0.65	0.906	292
15	0.09	0.70	0.907	336
16	0.10	0.60	0.904	206
17	0.10	0.65	0.902	239
18	0.10	0.70	0.904	275

For worst-case scenario maximum required number of pairs is 1037. Taking into account a possible dropout of 25%, to reach study objectives in regard to this endpoint, it is recommended to enrol at least 1383 patients into the study.

As well as for the primary objective, sample size was calculated for the secondary objective of the study: to evaluate the effect of Vipidia® on glycosylated hemoglobin (HbA1c) level dynamics in patients with diabetes mellitus type 2 (V3) in dependence of baseline clinical characteristics. According to concurrent Guidance for Industry for Diabetes Mellitus primary endpoint analysis (change from baseline in glycosylated hemoglobin (HbA1c) level on Vipidia® therapy (V3) in subgroups with different baseline clinical characteristics) should account for factors with substantial correlation with the outcome and independence from the treatment (e.g. prior therapy of DM, sex, age group, cardiovascular risk group, therapy type (monotherapy or combined therapy) etc.).

Taking into account inclusion criteria (either newly diagnosed DM type 2 (drug naive) or inadequate glycemic control on previously prescribed monotherapy with metformin or inadequate glycemic control on previously prescribed monotherapy with any other oral antidiabetic drug) as well as non-intervention nature of the study it is proposed to use regression model to determine factors related to effect of Vipidia® on glycosylated hemoglobin (HbA1c) level dynamics. Sample size was calculated using SAS 9.3 proc power procedure (power for Multiple Linear Regression) for following parameters (fixed scenario elements):

Fixed Elements	Scenario
Method	Exact
Model	Random X
Number of Predictors in Full Model	7
Number of Test Predictors	1
Partial Correlation	0.1
Nominal Power	0.9
Alpha	0.05

Where the computational method set to exact, assumed distribution of the tested predictors set to joint multivariate normal distribution for the response and tested predictors, number of predictors in the full model, not counting the intercept assumed to be 7 (prior therapy of DM, sex, age, cardiovascular risk group, therapy type (monotherapy or combined therapy), baseline BMI, initial glycemic control), number of predictors in the reduced model, not counting the intercept assumed to be at least 1, level of significance of the statistical test set to 0.05, desired power of the test set to 0.9, partial correlation between the tested predictors and the response, adjusting for any other predictors in the model assumed to be at least 0.1 (small effect size).

For the denoted scenario, it is required to receive data from at least 1052 patients after the treatment of Vipidia® on glycosylated hemoglobin (HbA1c) level dynamics.

Computed N Total	
Actual Power	N Total
0.800	1052

Taking into account a possible dropout of 25%, to reach study objectives in regard to this endpoint, it is recommended to enrol at least 1403 patients into the study. Due to minimal difference between these two endpoints and number of subjects required, it is recommended to take bigger computed number of subjects (1403).

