Values with Z-score > 3.5 will be considered outliers for study variables considered normally distributed. Preliminary normality test (Shapiro–Wilk criterion) will be performed for these variables. In case if normality distribution hypothesis will be rejected based on Shapiro–Wilk test results, median and IQR (interquartile range) will be used for outlier identification. Values > 1.5 IQR far from median value will be considered outliers. No data will be excluded / modified based on outlier identification, however, additional medical context assessment for these data will be performed and data quality control / source verification check will be considered.

Interim Analyses

An interim analysis is planned to be performed as soon as first 350 patients have completed the study by achieving final study visit or discontinuing the study.

The reasons of performing this interim analysis is an importance of study data for medical society and commitment of the company to disclosure clinically relevant information to medical specialists.

At this level of the analysis study objectives listed in the sections 2.2.1-2.2.4 will be evaluated. The results will be provided according to reporting rules applicable for final statistical analysis and described in the Statistical Analysis Plan.

The interim analysis will be performed according to statistical procedures described in the sections # 05-10 of this Statistical Analysis Plan. No subgroup analyses are to be performed within interim analysis of the study.

The results of the interim analysis should be disclosed to public either through publication in medical scientific journal or within presentation at medical congress/conference.

After study is completed the complete study results are to be considered as prevailing the results of

interim analysis.

Multiple Comparisons/Multiplicity

When needed, corrections for multiplicity will be justified and performed according to Bonferroni. Overall alpha-level will be controlled and will not exceed 0.05. The interim analysis will not be taken into account within multiplicity adjustment procedure.

Examination of Subgroups

Some secondary endpoints will be analyzed in subgroups of patients with different clinical characteristics: demographic information, nicotine use, history of DM2T (see “EFFICACY ANALYSES” chapter).

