9.1. Statistical Analysis of the Primary Efficacy Variable(s)

Primary study outcome - change from baseline in glycosylated hemoglobin (HbA1c) level on Vipidia® therapy (V3). Taking into account inclusion criteria (either newly diagnosed DM type 2 (drug naive) or inadequate glycemic control on previously prescribed any oral antidiabetic drug) as well as non-intervention nature of the study it is proposed to use multifactorial regression model to determine factors related to effect of Vipidia® on glycosylated hemoglobin (HbA1c) level dynamics.

Change from baseline in glycosylated hemoglobin (HbA1c) level on Vipidia® therapy (V3) in subgroups with different clinical characteristics will be summarized using relevant descriptive statistics and analyzed using Multiple Linear Regression with following predictors: prior therapy of DM, sex, age, cardiovascular risk group, therapy type (monotherapy or combined therapy), baseline BMI, initial glycemic control, T2DM duration. No subgroup analyses will be performed within interim analysis of study data.

In addition, change from baseline in glycosylated hemoglobin (HbA1c) level will be assessed and evaluated using Mixed model repeated measures (MMRM) methodology [14, 15]. The multiple visits for each patient will be incorporated as repeated measures within each patient. Visit will be treated as a categorical predictor and baseline glycosylated hemoglobin (HbA1c) level and duration of T2 DM will be included as a covariate. An appropriate covariance structure will be selected to provide estimates (Least Square Means) of change from Baseline and to perform statistical analysis at Visit 3. The dose-response trend hypothesis test will be conducted using the appropriate contrast statement for a linear (ordinal dose) trend. In addition, Least Squares Means, the associated standard errors and 95% confidence intervals will be displayed by each individual dose group.

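### SAP section 2.4 reports an actual power of 0.800 for the regression sample size of 1052, but the stated inputs give 0.900; the N is right and the printed power is wrong

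*SAP*

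**What the plan says.** Section 2.4 contains two sample size calculations.

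- **Primary objective** (precision of the mean HbA1c change): the worst case needs 1037 pairs, which becomes 1383 enrolled after allowing for 25% dropout.
- **Regression objective** (factors related to the HbA1c change): PROC POWER for multiple linear regression, exact method, random X, one tested predictor, partial correlation 0.1. The scenario table gives a nominal power of 0.9, and the text repeats the settings: "level of significance of the statistical test set to 0.05, desired power of the test set to 0.9". On model size it says: "number of predictors in the full model, not counting the intercept assumed to be 7".

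The regression result is introduced with "For the denoted scenario, it is required to receive data from at least 1052 patients". The Computed N Total table below it has one row: actual power 0.800, N Total 1052. The SAP then inflates 1052 for 25% dropout to 1403 and adopts 1403 as the larger of the two enrolment figures.

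Section 9.1 specifies the regression with the seven predictors of section 2.4 plus an eighth. Its list ends "baseline BMI, initial glycemic control, T2DM duration".

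**The concern.** When N is solved for a nominal power of 0.9, the actual power at that N must be at least 0.9. A result row showing 0.800 contradicts the scenario above it. The other table in the same section behaves as expected: with a nominal probability of 0.9, all 18 actual values lie between 0.900 and 0.907.

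This calculation yields the adopted enrolment target of 1403. As printed, a reader cannot tell from the result whether the regression was sized for 80% or 90% power, and the wrong figure could be carried into the study report. Either the power is misprinted or the N belongs to another scenario, so the calculation has to be repeated to find out which.

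**Working it through.** **Inputs, all from section 2.4:** alpha 0.05; partial correlation ρ = 0.1; p = 7 predictors in the full model; 1 tested; exact method, random X; dropout 25%.

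**Formula.** The test of one predictor is an F test on 1 and N − 8 degrees of freedom. Given the predictors, its noncentrality is ρ²/(1 − ρ²) × W, where W is chi-square on N − 1 − 6 degrees of freedom. Power is the noncentral F tail probability averaged over W. Here ρ²/(1 − ρ²) = 0.01/0.99 = 0.0101.

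**Reproducing the plan's N at power 0.9:**

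- N = 1051: power 0.8998
- N = 1052: power 0.9001

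So 1052 is the smallest N that reaches 0.9, exactly as the SAP states.

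**N that goes with power 0.800:**

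- N = 787: power 0.7997
- N = 788: power 0.8002

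**Hand check by Fisher's z.** Power ≈ Φ(atanh(0.1) × √(N − 3 − 6) − 1.96), with atanh(0.1) = 0.1003.

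- N = 1052: 0.1003 × √1043 − 1.96 = 1.28, power 0.8998
- N = 788: 0.1003 × √779 − 1.96 = 0.84, power 0.7997

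**Can another setting explain 0.800 at 1052?**

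- Fixed X instead of random X gives 0.903.
- Two tested predictors give 0.835 and three give 0.784.
- Alpha 0.025 gives 0.841 and alpha 0.01 gives 0.747.
- To obtain 0.800 exactly, the partial correlation would have to be about 0.0865 or alpha about 0.016. The SAP states neither.

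**What depends on it for enrolment:**

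- Regression at 0.9: 1052/0.75 = 1402.7, so 1403
- Regression at 0.8: 788/0.75 = 1050.7, so 1051
- Primary objective: 1037/0.75 = 1382.7, so 1383

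The SAP takes the larger of the two objectives. At 90% that is 1403; at 80% it would be 1383, set by the primary objective. The difference is 1403 − 1383 = 20 enrolled, or 1052 − 1037 = 15 evaluable. The 1037 evaluable patients of the primary objective already give the regression a power of about 0.896.

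**Eighth predictor (T2DM duration, section 9.1).** With p = 8, power at 1052 is 0.8998 and the smallest N for 0.9 is 1053. Even 12 model degrees of freedom give 0.8987 at 1052.

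**The case against.** The strongest objection is that this is a one-cell slip without consequence. The intended power is stated correctly twice, anyone who reruns the inputs recovers 0.900, the calculation serves a secondary objective, and the study is non-interventional and mainly descriptive. Most of this stands: no sample size, endpoint or analysis changes. It does not remove the need to correct the cell, which is the reported result of the calculation behind the adopted target.

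Four stronger readings are tempting, and the SAP does not support them.

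- **The regression has only 80% power.** A reader might infer this from the cell. The stated inputs give 0.900 at 1052.
- **Enrolment is 352 patients too high** (1403 − 1051). This ignores the primary objective, which would hold enrolment at 1383 in any case.
- **1052 is really an 80% figure already inflated for dropout**, since 789/0.75 = 1052. The exact N for 80% with the stated 7 predictors is 788, which inflates to 1051. Section 2.4 also treats 1052 as data to be received and then inflates it to 1403.
- **Power falls short once multiplicity is considered.** Section 5 says "Overall alpha-level will be controlled and will not exceed 0.05", but it applies Bonferroni correction only when needed, and no section makes the regression coefficients a family to be corrected together.

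It can also be said that, with eight predictors, 1052 just misses 0.9 (1053 needed; 1053/0.75 = 1404 enrolled). That is correct, but it amounts to one patient and a power change in the fourth decimal. It is no reason to alter the target.

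**Conclusion.** The point holds as a reporting error. The actual power at N = 1052 is 0.900, not 0.800, a discrepancy of 10 percentage points in the printed figure. The evaluable N of 1052 and the enrolment of 1403 are correct for the stated scenario and stay as they are. At most 20 enrolled patients could ever have depended on the choice between 80% and 90%, because the primary objective sets a floor of 1383.

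This rests on the inputs exactly as section 2.4 lists them, with one coefficient tested at 0.05. The difference between seven predictors in section 2.4 and eight in section 9.1 is a genuine inconsistency, but an immaterial one: power at 1052 remains 0.90 to two decimals.

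**What to change.** In section 2.4, correct the actual power in the Computed N Total table to 0.900, preferably by pasting the rerun output. Keep 1052 evaluable and 1403 enrolled.

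Optionally, add T2DM duration to the predictor list in section 2.4 so that it matches section 9.1, change the predictor count to 8, and note that power at 1052 remains 0.90 to two decimals.

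The cost is one table cell and, if the optional edit is made, one sentence. Sample size, endpoints, analyses and data collection do not change.
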